4.6 Blinding/Unblinding

Not applicable.

4.7 Treatment Compliance

Treatment compliance will be monitored by drug accountability as well as the subject's medical record and eCRF.

4.7.1 Premedications

Antiemetic medications should not be routinely administered prior to dosing of nivolumab, ipilimumab, and BMS-986016 (relatlimab). See Section 4.7.7 for subsequent premedication recommendations following a study drug-related infusion reaction.

See [Section 4.3](#) for post-infusion medications for subjects at higher risk of respiratory complications (**Combo D only**). All subjects in Combo D will receive pre-infusion and post-infusion medication per the descriptions in [Section 4.7.7](#) of the protocol.

4.7.2 Management Algorithms for Immuno-oncology Agents

Immuno-oncology (I-O) agents are associated with adverse events that can differ in severity and duration than adverse events caused by other therapeutic classes. Nivolumab, ipilimumab, BMS-986016 (relatlimab), and daratumumab are considered immuno-oncology agents in this protocol. Early recognition and management of adverse events associated with immuno-oncology agents may mitigate severe toxicity. Management algorithms have been developed to assist investigators in assessing and managing the following groups of adverse events:

- Gastrointestinal
- Renal
- Pulmonary
- Hepatic
- Endocrinopathies
- Skin
- Neurological

The safety management algorithms are provided in [Appendix 2](#) of this protocol.

4.7.3 Dose Delay Criteria

Study drug administration (nivolumab, ipilimumab, and BMS-986016) should be delayed for the following:

- Grade 2 non-skin, drug-related adverse event, except for fatigue.
- Grade 3 skin, drug-related adverse event
- Grade 2 drug-related creatinine, AST, ALT, and/or total bilirubin
- Grade 3 drug-related fatigue, nausea, vomiting, and anemia (Combination Cohort C only)
- Grade 3 drug-related laboratory abnormality, with the following exceptions:
 - Grade 3 lymphopenia or asymptomatic amylase or lipase does not require a dose delay
 - Grade ≥ 3 AST, ALT, or total bilirubin will require dose discontinuation ([Section 4.7.6](#))
- All troponin elevations require a dose delay to allow for prompt cardiac evaluation (Combo C only)
- Any adverse event, laboratory abnormality, or intercurrent illness which, in the judgment of the investigator, warrants delaying the dose of study drug.
- Subjects receiving ipilimumab or BMS-986016 in combination with nivolumab that have drug-related toxicities that meet the criteria for dose delay, should have both drugs (nivolumab and either ipilimumab, or BMS-986016) delayed until retreatment criteria are met.
- Subjects who require delay of study treatment should be re-evaluated weekly or more frequently if clinically indicated and resume nivolumab dosing when re-treatment criteria are met.

For subjects receiving Combo D treatment, daratumumab dose should be delayed if any of the following criteria below are met, to allow for recovery from toxicity related to daratumumab. For subjects whose dose delay is not related to nivolumab, treatment with nivolumab may continue:

- Grade 4 hematologic toxicity, except for grade 4 lymphopenia
- Grade 3 or higher thrombocytopenia with bleeding
- Febrile neutropenia
- Neutropenia with infection, of any grade
- Grade 3 or higher non-hematologic toxicities with the following exceptions:
 - Grade 3 nausea that responds to antiemetic treatment within 7 days
 - Grade 3 vomiting that responds to antiemetic treatment within 7 days
 - Grade 3 diarrhea that responds to antidiarrheal treatment within 7 days
 - Grade 3 fatigue that was present at baseline or that lasts for <7 days after the last administration of daratumumab
 - Grade 3 asthenia that was present at baseline or that lasts for <7 days after the last administration of daratumumab

Table 4.7.3-1: Daratumumab Dose Delay Guidance

| Week | Frequency | Dose Held | Dosing Re-start |
|------|-----------------------|-----------|--|
| 1-8 | Weekly (q1wk) | >3 days | next planned weekly dosing date |
| 9-24 | Biweekly (q2wks) | >7 days | next planned biweekly dosing date |
| 25+ | Every 4 weeks (q4wks) | >14 days | next planned every 4 weeks dosing date |

- Subjects experiencing a Grade 3 infusion reaction related to daratumumab must permanently discontinue daratumumab.
- Any adverse event deemed to be related to daratumumab that requires a dose hold of more than 3 consecutive planned doses will result in permanent discontinuation of daratumumab. If a dose delay occurs, then pharmacokinetic and pharmacodynamic assessments should be performed on the actual day of study drug administration, not on the original scheduled administration day
- Subjects who miss ≥ 3 consecutive planned doses of daratumumab for reasons other than toxicity should be withdrawn from study drug, unless, upon consultation with the sponsor and the review of safety and efficacy, continuation is agreed upon. Subjects who are withdrawn from daratumumab may continue to receive nivolumab.
- Any adverse event, laboratory abnormality, or intercurrent illness which, in the judgment of the investigator, warrants delaying the dose of study drug.

Doses of daratumumab may be delayed up to 4 weeks during Weeks 1-24 or up to 6 weeks from Week 25 and beyond. Any adverse event deemed to be related to daratumumab that requires a dose hold longer than those specified above will result in permanent discontinuation of daratumumab. If a dose delay occurs, then pharmacokinetic and pharmacodynamic assessments

should be performed on the actual administration day of daratumumab, not on the original scheduled administration day.

Administration of daratumumab may be restarted upon recovery from toxicity to Grade 2 or baseline, with the exception that Grade 2 laryngeal edema or Grade 2 bronchospasm must be fully recovered.

If daratumumab administration does not commence within the prespecified window ([Table 4.7.3-1](#)) of the scheduled administration date, then the dose will be considered a missed dose. Administration may resume at the next planned dosing date. A missed dose will not be made up.

Rescheduling (Combo A or B):

- Nivolumab may be delayed until the next planned ipilimumab dose if the next ipilimumab dose is scheduled within the next 12 days. This will permit periodic ipilimumab dosing to be synchronized with nivolumab dosing.
- Ipilimumab should be dosed at the specified interval regardless of any delays in intervening nivolumab doses. However, in order to maintain periodic synchronized dosing of ipilimumab and nivolumab, the dosing days of nivolumab and ipilimumab may be adjusted within the permitted +/- 3 day window, as long as consecutive nivolumab doses are given at least 12 days apart. Ipilimumab may be delayed beyond the 3 day window if needed to synchronize with the next nivolumab dose.
- A dose delay of ipilimumab which results in no ipilimumab dosing for > 12 weeks requires ipilimumab discontinuation, with exceptions as noted in [Section 4.7.6](#).

4.7.4 Dose Reductions

There will be no dose reductions for nivolumab, ipilimumab, BMS-986016 or daratumumab.

4.7.5 Criteria to Resume Dosing

Subjects may resume treatment with study drug when the drug-related AE(s) resolve(s) to Grade 1 or baseline, with the following exceptions:

- Subjects may resume treatment in the presence of Grade 2 fatigue.
- Subjects who have not experienced a Grade 3 drug-related skin AE may resume treatment in the presence of Grade 2 skin toxicity.
- For participants with Grade 2 AST, ALT and/or Total Bilirubin Abnormalities, dosing may resume when laboratory values return to baseline and management with corticosteroids, if needed, is complete.
- Drug-related pulmonary toxicity, diarrhea, or colitis must have resolved to baseline before treatment is resumed. Subjects with persistent Grade 1 pneumonitis after completion of a steroid taper over at least 1 month may be eligible for retreatment if discussed with and approved by the BMS Medical Monitor.
- Subjects who received systemic corticosteroids for management of any drug-related toxicity must be off corticosteroids or have tapered down to an equivalent dose of prednisone ≤ 10 mg/day.

- Drug-related endocrinopathies adequately controlled with only physiologic hormone replacement may resume treatment after consultation with the BMS Medical Monitor. Adrenal insufficiency requires discontinuation regardless of control with hormone replacement.
- Troponin elevations will require the participant to undergo a cardiac evaluation. Following this evaluation, determination of further treatment will be based on the discussion with the BMS medical monitor/designee.
- Dose delay of nivolumab, BMS-986016 and ipilimumab (Combo B), which results in treatment interruption of > 6 weeks requires treatment discontinuation, with exceptions as noted in Section 4.7.6.
- Dose delay of ipilimumab in Combo A, which results in treatment interruption of > 12 weeks requires treatment discontinuation, with exceptions as noted in Section 4.7.6.
- Ipilimumab may not be resumed sooner than 6 weeks (+/- 3 days) after the prior ipilimumab dose for Combo A.
- In general, subjects who meet criteria to resume ipilimumab will also have met criteria to resume nivolumab, so it should be feasible to synchronize dosing of both drugs when resuming ipilimumab. In order to facilitate this, the dosing days of nivolumab and ipilimumab may be adjusted within the permitted +/- 3 day window, as long as consecutive nivolumab doses are given at least 12 days apart.
- One exception to note is when ipilimumab and nivolumab doses are delayed due to drug-related Grade 3 amylase or lipase abnormalities not associated with symptoms or clinical manifestations of pancreatitis. If the investigator assesses the Grade 3 amylase or lipase abnormality to be related to ipilimumab and not related to nivolumab, nivolumab may be resumed when the amylase or lipase abnormality resolves to Grade < 3 but ipilimumab may only be resumed when the amylase or lipase abnormality resolves to Grade 1 or baseline. Investigator attribution of this toxicity to the ipilimumab dosing must be clearly noted in the subject's medical chart. The BMS Medical Monitor should be consulted prior to resuming nivolumab in such subjects.
- Subjects may resume treatment with daratumumab in Combo D, when the toxicity has resolved to Grade 2 or baseline, with the exception that Grade 2 laryngeal edema or Grade 2 bronchospasm must be fully recovered. If the daratumumab administration does not commence within the pre-specified window of the scheduled administration date, then the dose will be considered a missed dose. Administration may resume at the next planned dosing date.

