Subjects who complete the neoadjuvant portion of the study and complete standard of care treatment post-surgery/biopsy who develop unresectable recurrent or metastatic disease within 1 year of surgical resection, or completion of standard of care (whichever is later), may receive treatment with nivolumab monotherapy, if eligible. Eligibility assessments are detailed in [Table 5.1-5](#).

Please refer to the Pharmacy Manual for more detail. There are no pre-medications recommended on the first cycle, **except for Combo D**. All subjects in Combo D will receive pre-infusion and post-infusion medication per the descriptions in [Section 4.7.7](#) of the protocol. If an acute infusion reaction is noted, subjects should be managed according to Section 4.7.7.

Dosing modifications:

There will be no dose modifications allowed for the management of toxicities of individual subjects.

Dosing window:

When nivolumab is administered alone and in combination with BMS-986016 (relatlimab), subjects may be dosed no less than 12 days between doses during Q2 week dosing. For ipilimumab (Combo A), subjects may be dosed within a \pm 1-week window and no less than 5 weeks from the previous dose. For subjects in Combo B, when nivolumab is administered in combination with ipilimumab, subjects may be dosed within a \pm 3-day window and no less than 18 days from the previous dose. A dose given more than 3 days after the intended dose date will be considered a delay, except for subjects receiving ipilimumab in Combo A. A maximum delay of 6 weeks between doses is allowed, except for subjects in the Neoadjuvant cohort.

Daratumumab will be administered at a dose of 16 mg/kg as an IV infusion every week for the 8 doses (-1 and +3 days window is allowed), every two weeks from weeks 9 to 24 (can be delayed up to 1 week) and every four weeks from weeks 25 onwards (can be delayed up to 14 days) until toxicity or disease progression.

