 - Grade 4 drug-related endocrinopathy adverse events such as hyper- or hypothyroidism, or glucose intolerance, which resolve or are adequately controlled with physiologic hormone replacement (steroids, thyroid hormones) or glucose-controlling agents, respectively, may not require discontinuation after discussion with and approval from the BMS Medical Monitor.
- Daratumumab treatment should be permanently discontinued for the following reasons:
 - Grade 4 infusion reactions related to daratumumab.
 - For Grade 3 infusion reactions related to daratumumab: Once reaction symptoms resolve, consider restarting the infusion at no more than half the rate at which the reaction occurred. If the patient does not experience additional symptoms, resume infusion rate escalation at increments and intervals as outlined in **Table 4.3-1**. Repeat the procedure above in the event of recurrence of Grade 3 symptoms. Permanently discontinue daratumumab upon the third occurrence of a Grade 3 or greater infusion reaction
- Any adverse event, laboratory abnormality, or intercurrent illness which, in the judgment of the Investigator, presents a substantial clinical risk to the subject with continued study drug dosing.

- Any event that leads to delay in dosing lasting > 6 weeks for Combo B and C, and > 12 weeks for Combo A from the previous dose requires discontinuation, with the following exceptions:
 - Dosing delays to allow for prolonged steroid tapers to manage drug-related adverse events are allowed.
 - Dosing delays lasting > 6 weeks (Combo A and C) or >12 weeks (Combo A) from the previous dose that occur for non-drug-related reasons may be allowed if approved by the BMS medical monitor.

For Combo A, B, and C, prior to re-initiating treatment in a subject with a dosing delay lasting > 6 weeks (Combo B and C) and > 12 weeks (Combo A), the BMS medical monitor must be consulted. Tumor assessments should continue as per protocol even if dosing is delayed. Periodic study visits to assess safety and laboratory studies should also continue every 6 weeks or more frequently if clinically indicated during such dosing delays.

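### The protocol gives both 6-week and 12-week limits for permanently stopping Combo B ipilimumab and Combo A nivolumab after a dosing delay

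*Protocol*

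**What the plan says.** The limit on a dosing delay appears in four protocol sections and once in the SAP.

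- **Protocol 4.5, dosing window:** "A maximum delay of 6 weeks between doses is allowed, except for subjects in the Neoadjuvant cohort". No drug or metastatic arm is singled out.
- **Protocol 4.7.3**, under a sub-heading that opens "Rescheduling (Combo A or B": "A dose delay of ipilimumab which results in no ipilimumab dosing for > 12 weeks requires ipilimumab discontinuation".
- **Protocol 4.7.5:** "Dose delay of nivolumab, BMS-986016 and ipilimumab (Combo B), which results in treatment interruption of > 6 weeks requires treatment discontinuation". The next bullet gives one drug in one arm a longer limit: "Dose delay of ipilimumab in Combo A, which results in treatment interruption of > 12 weeks requires treatment discontinuation".
- **Protocol 4.7.6** sets its limit by arm and counts from the previous dose: "Any event that leads to delay in dosing lasting > 6 weeks for Combo B and C, and > 12 weeks for Combo A". It has two exceptions. The first is "Dosing delays to allow for prolonged steroid tapers to manage drug-related adverse events are allowed". The second covers delays unrelated to study drug, if the medical monitor approves: "Dosing delays lasting > 6 weeks (Combo A and C) or >12 weeks (Combo A) from the previous dose". The paragraph that follows requires the monitor to be consulted before restart beyond 6 weeks in Combos B and C and beyond 12 weeks in Combo A. The section then says that discontinuation is judged drug by drug, except that both drugs stop together in Combo C.
- **SAP 7.4.2.1** gives a maximum of 6 weeks, counted from the last dose, for all treatment without distinction of arm or drug.

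**The concern.** These are rules for stopping a drug permanently. A site that reads one section would stop, and a site that reads another would find no requirement to stop, for the same drug after the same gap. The scope differs as well: 4.7.3 ends ipilimumab only, whereas 4.7.5 speaks of ending treatment.

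Patient safety and consistent conduct across sites are at stake. Three planned summaries also depend on how the rule is applied: reasons for discontinuation (SAP 7.3.1), and duration of treatment and relative dose intensity (SAP 7.4.1). For Combo A, the central check in 4.7.6 does not apply until 12 weeks. A site following that section could restart nivolumab at, say, 10 weeks without the consultation, although 4.7.5 requires discontinuation.

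**Working it through.** The plan has no figure to reproduce here. The check sets the limits side by side and tests whether different ways of counting time could reconcile them.

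**1. Who is covered by the 4.7.5 six-week bullet.** It lists nivolumab, BMS-986016 and ipilimumab, with Combo B in brackets. BMS-986016 is not given in Combo B, so the bracket cannot qualify the whole list. It qualifies ipilimumab, and nivolumab is covered in every arm. The next bullet reserves 12 weeks for Combo A ipilimumab, which leaves Combo A nivolumab at 6.

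**2. Limits by source.**

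| Source | Combo B ipilimumab | Combo A nivolumab |
|---|---|---|
| Protocol 4.5 | 6 weeks | 6 weeks |
| Protocol 4.7.3 | > 12 weeks | not addressed |
| Protocol 4.7.5 | > 6 weeks | > 6 weeks |
| Protocol 4.7.6 | > 6 weeks | > 12 weeks (arm named, no drug named) |
| SAP 7.4.2.1 | 6 weeks | 6 weeks |

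**3. Could different clocks explain it?** 4.7.6 and the SAP count from the last dose given, and 4.7.3 counts time without ipilimumab. Suppose that the six weeks in 4.5 and 4.7.5 start only at the missed date:

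- Combo A nivolumab, every 2 weeks: 2 + 6 = 8 weeks from the previous dose, which is 12 − 8 = 4 weeks short of the 4.7.6 limit.
- Combo B ipilimumab, every 3 weeks: 3 + 6 = 9 weeks, which is 12 − 9 = 3 weeks short of the 4.7.3 limit. Against 4.7.6, which counts from the previous dose, the difference stays at 12 − 6 = 6 weeks.

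The clocks can narrow the window but do not close it.

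**4. Two worked cases, each 10 weeks after the previous dose and outside the exceptions.**

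- Combo A nivolumab: 10 weeks from the last dose, or 10 − 2 = 8 from the missed date. Both exceed 6, so 4.7.5 requires discontinuation. Since 10 does not exceed 12, 4.7.6 requires neither discontinuation nor consultation on account of the delay.
- Combo B ipilimumab during induction: 10 weeks, or 10 − 3 = 7 from the missed date. Both 4.7.5 and 4.7.6 require discontinuation; 4.7.3 does not.

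**5. Extent of the window.** Counted from the previous dose, it runs from day 43 (6 × 7 = 42, plus 1) to day 84 (12 × 7). At 6 weeks or less no section requires stopping because of delay. Beyond 12 weeks the discontinuation rules agree, subject to the exceptions.

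**6. The exception wording.** The exception for delays unrelated to study drug names Combo A under both limits and omits Combo B. The paragraph after it pairs 6 weeks with Combos B and C and 12 weeks with Combo A, as the main rule does.

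**The case against.** **The shorter rule governs.** Every line cited is either a requirement to stop or a maximum, and none expressly permits dosing at 7 to 12 weeks. A site that always applied the shorter limit would break no sentence. That is true, but no section says that the shorter limit prevails, and on that reading the 12-week text would have no effect for these two drugs. The Combo A consultation threshold in 4.7.6 also refers to restarting treatment in general, not to ipilimumab alone.

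**The 4.7.3 sub-heading may simply be too broad.** The neighbouring bullet about intervening nivolumab doses fits the Combo A schedule; in Combo B induction both drugs are given together every 3 weeks. This is a plausible account of how the conflict arose, but sites follow the text as issued, and only the sponsor can say what was meant.

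**The exception label is a slip.** Agreed: the next paragraph of 4.7.6 shows as much. It still needs correcting, because read literally Combo B has no exception for delays unrelated to study drug, but it is a secondary point.

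**The consequences are limited.** This largely stands. Steroid-taper delays are exempt, discontinuation is judged drug by drug, and Combo B ipilimumab is only four doses, so that conflict arises during induction only. The study is non-comparative. ORR uses all treated subjects, its window does not end when treatment stops, and scans continue through delays and after discontinuation. The documents therefore do not support an inference that the primary estimate is invalid.

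**Conclusion.** The contradiction is real and confined to two cases: Combo B ipilimumab (12 weeks in 4.7.3 against 6 elsewhere) and Combo A nivolumab (12 weeks in 4.7.6 against 6 elsewhere). It applies to gaps of more than 6 and up to 12 weeks outside the 4.7.6 exceptions. Because it is a permanent stopping rule that bears on patient safety, it should be corrected. This rests on the current text of Revised Protocol 07 and SAP version 4.0, and on reading the Combo B bracket in 4.7.5 as attached to ipilimumab.

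The number of subjects affected is unknown, because the documents give no rate of holds of this length. Four stronger readings are tempting but not supported:

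- **That every delay of 6 to 12 weeks is affected.** Combo B nivolumab, Combo C and monotherapy have no 12-week limit anywhere, and the exceptions remove further cases.
- **That about 40 of 110 cervical Combo B subjects would meet the conflict** (0.364 × 110 = 40). The 36.4% in Protocol 1.4.2.2 is the share of pooled melanoma subjects who stopped because of drug-related adverse events. It is not a rate of long holds.
- **That the planned sizes measure exposure to the conflict** (5 × 40 = 200 in Combo A, about 110 cervical in Combo B). They are planned arm sizes, and randomization of anogenital subjects closed with Revised Protocol 06.
- **That monotherapy has no limit because 4.7.6 omits it.** Protocol 4.5 and 4.7.5 already set 6 weeks there.

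**What to change.** Replace the scattered limits in Protocol 4.5, 4.7.3, 4.7.5 and 4.7.6 with one table by arm and drug, and have each section refer to it. For each row state the delay limit, the event from which the delay is counted, what is discontinued (one drug or all treatment, consistent with the drug-by-drug rule in 4.7.6), which exceptions apply, and when the medical monitor must be consulted. Correct the arm label in the exception for delays unrelated to study drug. Then align the single six-week sentence in SAP 7.4.2.1 with that table; a correction to the protocol alone would leave the SAP in conflict.

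The sponsor's clinical team decides the limits, and this review proposes none. The cost is protocol wording or an administrative letter plus one SAP sentence, with no new data and no change to an analysis. The by-subject dosing listing already planned in SAP 7.4.1 can show how many gaps of 43 to 84 days occurred in the two affected cases.
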